Advances in trauma care have reduced infection rates in tibial plateau fractures from $80\%^{10}$ to $10 - 14\%^{11}$, but the complex nature of the injury has been shown to be an independent risk factor for infection¹². Preventing colonization of the bone graft used in tibial plateau fractures is desirable. The ability to provide antibiotics locally, rather than systemically, for the duration of the graft remodeling may improve outcomes of this injury if bony healing is not compromised.

We propose a prospective clinical trial of tibial plateau fractures treated with internal fixation and a calcium sulfate graft which can be mixed with antibiotics and molded into various bead sizes for implantation into bone defects. The graft material chosen for this study is STIMULAN Rapid Cure (Biocomposites, UK), which is approved for use as a bone void filler and may be mixed with a variety of antibiotics. The combination of STIMULAN + antibiotic in bead form is herein referred to as the "study device".

Why is a Trial Needed Now?

While studies have been done to look at prevention and treatment of infection with the study device¹³⁻²⁵, there is no published evidence of its effectiveness in acute, closed, non-infected tibial plateau fractures. Previous studies have indicated that calcium sulfate is resorbed by three months after implantation and that bone has remodeled by six months²⁶⁻²⁷. These studies did not include the use of antibiotics in the calcium sulfate.

Study Aims

Our primary study aim is to look at resorption and remodeling of the study device into bone. Another important aim of the study is to look at subsidence, or collapse, of the joint surface. Secondary outcomes are those that are clinically important after this injury including time to bone healing, knee range of motion, knee stability, return to work and activities, infection, wound problems, functional outcomes, and complications.

How Will the Results of This Trial Be Used?

This trial will provide clinical evidence on the use of antibiotics mixed with calcium sulfate in the treatment of acute, closed, non-infected tibial plateau fractures. This will guide orthopaedic surgeons in their clinical decision making for this complex injury.

Methods

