This will be a prospective, non-randomized study. Up to four centers in Canada with extensive experience in the treatment of tibial plateau fractures will be selected for this multi-centre study. The study will be an investigator-driven study with QEII Health Sciences Centre as the lead site. It will be supported by an unrestricted research grant from Biocomposites Ltd. with the funds being distributed to all sites via the lead site. Thirty (30) consecutive patients who meet the inclusion criteria will be recruited for the study and followed for one year.

Inclusion Criteria:

Patient selection criteria will include:

- Adult (skeletally mature) men or women;
- Acute, closed, tibial plateau fractures, Schatzker grade 1 through 5;
- Internal fixation and use of study device per protocol;
- Fracture repair within 30 days of injury;
- Signed informed consent to participate in study.

Exclusion Criteria:

- Uncontrolled diabetes;
- Severe degenerative or metabolic bone disease;
- Malignancy;
- Severe vascular or neurologic disease;
- Alcoholism;
- Substance abuse;
- Use of systemic steroids;
- Immunosuppressive therapy;
- Hypercalcaemia;
- Renal-compromised patients;
- Osteomyelitis or chronic infection in the study limb;
- Women who are pregnant or breast-feeding.

All sites will obtain approval from the institutional review board at their respective hospitals and participants will be required to provide informed consent prior to any study procedures. Since the study device is an option for treatment of this injury, informed consent may occur post-operatively if the study device was used per protocol as the standard of care. Patients who consent to participate in study but do not receive the study device will not be considered study participants.

All visits required will be those as per regular follow up visits in their institutions, so no travel expenses should be required. If however extra visits are required for study purposes (e.g. CT scan performed after hours), a small stipend will be paid to cover parking/ travel.

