Standard open reduction and internal fixation techniques will be used to restore fracture stability. The implants utilized for this purpose will include locked and unlocked premolded proximal tibial plates and small fragment plates as per the decision of the attending surgeon. Subarticular grafting with the study device will be accomplished via an open procedure. The study device cannot be used alone or with screws only, it must be used with standard internal fixation as noted above.

Preparation of the Study Device

The study device is to be prepared with the antibiotic chosen according to the manufacturer's mixing guidelines (Appendix A). The selection of antibiotic from those in the mixing guidelines is left to the surgeon's discretion. A maximum of one 10cc kit of STIMULAN Rapid Cure per participant is to be used. The STIMULAN is to be prepared in bead form. The selection of bead size is at the discretion of the surgeon.

Post-operative immobilization, weight-bearing, and rehabilitation protocol will be the standard of care for each surgeon.

Follow-up will be scheduled at 6 weeks, 3 months, 6 months, and 12 months as per the usual at each site. Other visits may be "clinically indicated" but would not be required as a part of this study. Baseline information will be collected during the initial hospital stay.

Risks and Benefits of Study Participation

This trial does not involve any experimental devices or procedures. The risks of participating are no greater than standard of care. As with any study, there is a risk of breach of confidentiality. There is no direct benefit to participants in this study. The results of this study will benefit future patients with this injury by providing more evidence on treatment with the study device.

How Will The Outcome Measures Be Measured at Follow-up?

Basic demographic information: At the time of study inclusion, information on basic demographics (age, sex), past medical history, co-morbidities, medications (i.e. bisphosphonates, vitamin D), pre-injury level of activity and/or employment and mechanism of injury will be collected for all participants.

Functional outcomes: The Knee injury Osteoarthritis Outcome Score (KOOS)²⁸ is a validated self-administered questionnaire which will be completed at the designated follow-up visits. The questionnaire completion time is approximately 15 minutes. Return to work and return to preinjury activities will be measured in weeks.

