Clinical outcome: Range of motion will be evaluated and will include active and passive flexion and extension. Knee stability will be assessed. The surgical site will be examined for progression in healing, wound issues (drainage, dehiscence, etc.) or signs of infection.

Radiological outcome: Evaluation will be performed at each participating centre and all radiographs will be sent to the principal investigation centre with all identifiers removed. Exams at each study visit will be the standard AP and lateral radiographs. Amount of study device remaining and percent remodeled will be measured on plain radiographs. Time to union will be defined as bridging callus evident on two x-rays. Our previous study on tibial plateau fractures indicated that subsidence occurs between three and six months after surgery²⁹. Therefore, at six months a CT scan will be performed to determine if any study device remains and to measure any subsidence of the joint surface.

Adverse Events: Since the study device is being used according to the indications for use, monitoring of adverse events will be according to standard clinical practice. Reporting of serious adverse events will be according to the REB policy at participating sites, with copies sent to the lead site and the Quality Department at Biocomposites. Adverse events of interest in the study are those associated with the surgical procedure and healing of the injury.

Data Collection, Management, and Retention

Each study participant will be assigned a unique Subject ID to safeguard confidentiality. The Subject ID will be used on all data collection forms. Subject IDs will be assigned consecutively at each site. Participating sites will be provided with a site number and all the required Case Report Forms prior to initiation. Completed CRFs and questionnaires from each study site will be sent via Fax or e-mail to the lead site after each patient follow-up visit, according to the data transfer and/or sub-site agreement in effect. Sites will also be given the option to enter deidentified data directly into REDCap. Study sites will keep the originals and file them in the subject binder at each site. Radiographic images (x-rays and CT) for each subject will be deidentified and copied onto a compact disc (CD) and submitted to the lead site at the end of the study. See Appendix B for schedule of events.

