Data management will be coordinated from the lead site (QEII Health Sciences Centre). Study data will be managed using REDCap electronic data capture tools hosted by Nova Scotia Health Authority. REDCap (Research Electronic Data Capture) is a secure, web-based application designed to support data capture for research studies, providing 1) an intuitive interface for validated data entry; 2) audit trails for tracking data manipulation and export procedures; 3) automated export procedures for seamless data downloads to common statistical packages; and 4) procedures for importing data from external sources. Sites will be given a choice to either continue to send CRF's to the lead site or they will be given dedicated login information and training on how to access the REDCap tool and enter data directly into REDCap.

Study documents will be retained for seven (7) years. Sites will store and maintain all study-related documents according to local policies, guidelines, and standards. Destruction of study records will be in accordance with local policies.

Analysis of Results

All analysis will be performed at the lead site. Descriptive statistics will be used to describe the study sample. Patients will be evaluated as to union, subsidence, loss of graft or premature resorption, percent of graft remaining at each visit, knee range of motion, knee stability, loss of fixation or fixation failure, infection, functional recovery (outcome scores and return to work, return to activity) and effect of tobacco use, age, sex, fracture classification. The sample size of thirty participants was chosen based on the expected recruitment rate at this site and others planning to participate in the interest of providing objective evidence of the healing potential with this device in patients with this injury.

References

- 3. Segal, D., A. V. Franchi, et al. (1985). "Iliac autograft for reconstruction of severely depressed fracture of a lateral tibial plateau. Brief note." *J Bone Joint Surg Am* 67(8): 1270-2.
- 4. Younger, E., Chapman, MW (1989). "Morbidity at bone graft donor sites." *J. Orthop Trauma* 3: 192-195.

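### Does the percent of graft remaining lack a usable 100%, because the plan names no reference film or implanted amount?

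*Combined protocol and SAP*

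**What the plan says.** Under Study Aims: "Our primary study aim is to look at resorption and remodeling of the study device into bone". The radiological outcome paragraph gives the measurement: "Amount of study device remaining and percent remodeled will be measured on plain radiographs". It also says who reads the films and where they go: "Evaluation will be performed at each participating centre and all radiographs will be sent to the principal investigation centre". Analysis of Results then lists "loss of graft or premature resorption, percent of graft remaining at each visit" and places all analysis at the lead site.

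On what was implanted, Preparation of the Study Device sets only a ceiling: "A maximum of one 10cc kit of STIMULAN Rapid Cure per participant is to be used". On timing, the same part of the protocol says "Baseline information will be collected during the initial hospital stay". Appendix B schedules AP and lateral films at Baseline, 6 weeks, 3, 6 and 12 months, without saying on which side of the operation Baseline falls. The Methods section allows consent on either side, since "informed consent may occur post-operatively if the study device was used per protocol as the standard of care".

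**The concern.** A percent needs a denominator, and none is written down. Three candidates come to mind, and each is left open. The implanted volume is capped but not named as a recorded item. The Baseline film could serve only if taken after implantation, because an injury film shows no graft. The six-month CT has no earlier CT to compare with.

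If Baseline were the injury film, the first scheduled film showing the device would be at 6 weeks. Taking that as 100% hides all earlier resorption and inflates every later percent. The literature figure cited under Why is a Trial Needed Now?, resorption by three months, is timed from implantation, so the comparison would be distorted. Up to four centres evaluate their own films, and if they chose different references the pooled figure would mix scales. All this would fall on the primary aim.

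**Working it through.** The plan gives no figure for this outcome, so there is nothing to reproduce. The check has two parts: how large the error could be under the worst reading, and whether the plan supports that reading.

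**Size under a 6-week reference.** Visit times are taken as 6, 13, 26 and 52 weeks. The resorption curves are assumptions; only the three-month figure comes from the protocol, and it was reported for calcium sulfate without antibiotic. With linear loss to zero at week L, the fraction left is 1 − t/L. A 6-week reference multiplies each later percent by 1/f, where f is the fraction left at 6 weeks.

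| Assumed loss | f at 6 weeks | True 3-month value | 3-month value against 6-week film |
|---|---|---|---|
| Linear, L = 13 | 1 − 6/13 = 53.8% | 0% | 0% |
| Linear, L = 26 | 1 − 6/26 = 76.9% | 50.0% | 50.0/76.9 = 65.0% |
| Linear, L = 52 | 1 − 6/52 = 88.5% | 75.0% | 75.0/88.5 = 84.8% |
| Exponential, 5% left at week 13 | 0.05^(6/13) = 25.1% | 5.0% | 5.0/25.1 = 19.9% |

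For L = 52 the 6-month value reads 50.0/88.5 = 56.5% instead of 50.0%. For L = 26, if half the patients were scored each way, the pooled 3-month mean would be (50.0 + 65.0)/2 = 57.5%. In the first row, which matches the protocol's own resorption time, only the 6-week visit is affected (100% read for a true 53.8%); from 3 months on both references give zero.

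**Size under a post-operative reference.** Here f is replaced by 1 and the error is zero at every visit.

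**Which reading the plan supports.**

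- Use of the study device is an inclusion criterion, and the Methods section says patients who consent but do not receive it are not participants. Inclusion cannot be confirmed until implantation.
- Baseline lies within the initial hospital stay, which includes the days after surgery.
- Appendix B marks adverse-event assessment at Baseline. The Adverse Events paragraph defines the events of interest as those tied to the operation and to healing, so Baseline reasonably extends past surgery.
- The entry criterion "Acute, closed, tibial plateau fractures, Schatzker grade 1 through 5" needs an injury image, but nothing requires that image to be the scheduled Baseline film. It does not point to a pre-operative Baseline.

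These passages do not prove that the Baseline film is post-operative. They make it the more natural reading.

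**Is the implanted volume needed?** A volume in cc cannot be compared directly with a two-dimensional film, so it could be only a cross-check. Its absence from the text is also weak evidence that it is not recorded: the list that omits it is headed as basic demographic information, and tobacco use, which is analysed, is not named there either. The case report forms are not among the documents.

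**Is premature resorption lost?** No. It is listed separately from the percent remaining. A 6-week film with no visible graft can be scored as resorbed without any ratio.

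**The case for a change.** The strongest case for a change is that a plausible reading is not a definition. Even if the Baseline film is post-operative, no sentence names it as the comparator. Each centre does its own evaluation, and two careful readers could report different percents from the same films. The outcome carries the primary aim, and the cure would cost two or three sentences and a footnote to Appendix B.

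The textual part of this stands: the reference is unstated and the Baseline film is unlabelled. The claim of harm is weaker. It needs a pre-operative Baseline film, no use of any post-operative film taken in usual care, a 6-week reference that the plan never proposes, and resorption slower than the protocol expects or with a tail beyond three months. If centres did differ, the lead site receives the images and does all the analysis, so it can re-read them against one reference wherever a post-operative film exists. A patient with no such film would have an amount but no percent; that would limit the data, and writing down the definition would not supply the film.

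Antibiotic and bead size, left to the surgeon and not named as recorded items, are a separate reporting matter. They do not bear on the denominator, and the case report forms may cover them.

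**Conclusion.** The gap in wording is real, but no change to the plan follows. No stated rule gives a wrong result. The device visible on the first film after implantation is the obvious 100%, analysts would use it unprompted, and the error is then zero. The worst-case figures (65% for 50%, or 20% for 5%, at 3 months) are correct arithmetic, but they rest on assumed curves and on a reference the plan does not prescribe. Under the protocol's own resorption time even that reference changes nothing from 3 months on. The study is single-arm and descriptive, with 30 patients and no test, threshold or decision that depends on the percent.

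This conclusion assumes that most participants have a post-operative film during the hospital stay and that the lead site applies one reference across centres. The documents are consistent with both but state neither. The published report would need to say which film was taken as 100%.

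### Should resorption be analysed by antibiotic, bead size and implanted volume, given that the surgeon decides what is implanted?

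*Combined protocol and SAP*

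**What the plan says.** Under Study Aims: "Our primary study aim is to look at resorption and remodeling of the study device into bone". The Introduction / Background defines the study device as STIMULAN combined with antibiotic in bead form, and says the calcium sulfate "may be mixed with a variety of antibiotics". Under Why is a Trial Needed Now?, the earlier work on resorption and remodeling times is set apart from this study: "These studies did not include the use of antibiotics in the calcium sulfate".

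Preparation of the Study Device leaves two features open and limits a third:

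- Antibiotic: "The selection of antibiotic from those in the mixing guidelines is left to the surgeon's discretion".
- Bead size: "The selection of bead size is at the discretion of the surgeon".
- Volume: "A maximum of one 10cc kit of STIMULAN Rapid Cure per participant is to be used".

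The radiological outcome paragraph says "Amount of study device remaining and percent remodeled will be measured on plain radiographs", with a CT scan at six months to see whether any device is left. Analysis of Results promises a descriptive account of the sample, lists the outcomes (among them percent of graft remaining at each visit), and ends the list with the "effect of tobacco use, age, sex, fracture classification". It states no test, model or significance level. The 30 patients were chosen on expected recruitment.

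**The concern.** The antibiotic is the new element, yet the factor list holds only patient and injury characteristics. One label, study device, covers every permitted combination of antibiotic, bead size and volume, and with up to four centres all three could differ between patients. If resorption depended on the mixture, the pooled figure would depend on what the surgeons happened to choose, and a surgeon reading the report could not tell which preparations it represents. The plan already intends to look at four factors in 30 patients, so small numbers alone do not explain leaving out the features closest to the primary aim. At stake would be how far the main descriptive result can be applied to a particular preparation.

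**Working it through.** **1. Factors against device features.** Listed factors: tobacco use, age, sex, fracture classification (4). Device features that can vary: antibiotic, bead size, volume (3). Overlap: 0 of 3. The observation is correct as a reading of the text.

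**2. What the aim requires.** The aim concerns the study device, which is defined as the combination with antibiotic, whichever antibiotic is used. The contrast drawn with earlier work is antibiotic-loaded against unloaded calcium sulfate. The protocol does not ask which antibiotic or bead size resorbs faster. A pooled estimate over the mixtures used therefore matches the stated aim.

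**3. How far pooling could matter.** The documents give no rates by preparation, so this is an assumed example. Let one preparation be 90% resorbed at a visit and another 50%, with share m of patients on the first. The pooled value is 0.9m + 0.5(1 − m):

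- m = 0.2: 0.18 + 0.40 = 58%
- m = 0.5: 0.45 + 0.25 = 70%
- m = 0.8: 0.72 + 0.10 = 82%

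Each is a correct description of the patients treated. A table of counts shows the mix behind it. The documents do not suggest that so large a contrast exists.

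**4. What a breakdown could show.** There is no planned figure to reproduce, because N = 30 rests on recruitment. Splits and SDs below are assumptions.

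Pooled mean, 95% half-width: t(0.975, 29)/√30 = 2.045/5.477 = 0.37 SD.

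Two-group difference, 95% half-width: t(0.975, 28) × √(1/n₁ + 1/n₂), with t = 2.048:

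| Split | √(1/n₁ + 1/n₂) | Half-width (SD) | SD 10 points | SD 20 points | SD 30 points |
|---|---|---|---|---|---|
| 15 v 15 | 0.365 | 0.75 | 7.5 | 15.0 | 22.4 |
| 10 v 20 | 0.387 | 0.79 | 7.9 | 15.9 | 23.8 |
| 5 v 25 | 0.490 | 1.00 | 10.0 | 20.1 | 30.1 |

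Difference detectable with 80% power at two-sided 0.05: (1.960 + 0.842) × √(1/n₁ + 1/n₂) = 1.02 SD (15 v 15), 1.09 SD (10 v 20) and 1.37 SD (5 v 25).

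Six-month CT, if no patient has device left, exact 95% upper limit 1 − 0.025^(1/n): 11.6% for n = 30, 21.8% for n = 15, 52.2% for n = 5.

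More than two levels makes this worse. If there were three antibiotics and three bead sizes (assumed), 30/9 = 3.3 patients per combination.

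**5. Volume.** Percent of graft remaining is already relative to the amount implanted. That removes the starting quantity from the scale, though not any dependence of resorption time on volume.

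**The case for a change.** The best argument for a change is that it costs almost nothing. A check of the case report forms, a few fields from the operative note and a sentence or two in Analysis of Results would commit the report to showing which preparations were used and whether results looked alike. The trial is meant to guide surgeons, and they must choose an antibiotic and bead size. A general promise to describe the sample permits counts per antibiotic but does not oblige anyone to give resorption by antibiotic.

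That last point stands: the plan names no such breakdown. The rest carries less weight. The case report forms are not among the documents and the content of Appendix A does not appear in the available text, so it cannot be said that these features go unrecorded or how many mixtures were open to the surgeons. Nothing in the plan prevents an analyst from tabulating antibiotic and bead size, and an orthopaedic device series would ordinarily do so. Going from four exploratory factors to seven, over four follow-up visits, adds sparse cells in which the surgeon's choice may be confounded with surgeon, site and defect size. Such estimates could not establish that one mixture resorbs differently from another.

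**Conclusion.** The factual observation holds, but no change to the plan follows. Carried out as written, the analysis gives a valid description of resorption and remodeling for the study device as the protocol defines it. What is missing is reporting detail (how many patients received each antibiotic and bead size), which analysts can supply within the planned description of the sample.

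A formal addition would gain little. Against a pooled half-width of 0.37 SD, a comparison between two preparations would have 0.75 to 1.00 SD for splits from 15 v 15 to 5 v 25, so only very large differences would be visible, and those would be open to confounding.

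This rests on three assumptions: that the pooled device is the intended target, as its definition and the primary aim indicate; that the antibiotic and bead size can be recovered from the case report forms or operative notes, neither of which is in the documents; and that the illustrative splits and SDs are reasonable, since the documents give neither.
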